4.2. Eligibility Criteria

4.2.1. Inclusion Criteria

A patient will be eligible for inclusion in this study only if ALL of the following criteria apply:

- Men or women age 18 - 75 years;
- Diagnosis of moderate to severe active UC (including ulcerative proctitis if proximal extension of disease occurs beyond 10 cm) confirmed by endoscopy and histology at least 12 Weeks prior to screening visit. Moderate to severe active UC defined by Modified Mayo Score (MMS) of 5 to 9 inclusive (on a scale of 0-9). Moderate to severe active UC should be confirmed at screening visit with a centrally read endoscopy sub-score of at least 2 (on a scale of 0-3);
- Patients having either a documented inadequate response, no response, a loss of response, or an intolerance (defined as the occurrence of at least one Adverse Reaction leading to treatment discontinuation) to either immunosuppressant treatment (i.e., azathioprine, 6-mercaptopurine, methotrexate), tumor necrosis factor [TNF] inhibitors, vedolizumab, JAK inhibitors and/or corticosteroid treatment. Inadequate response, no response, loss of response is defined as:
 - Active disease or relapse in spite of thiopurines or methotrexate given at an appropriate dose for at least 3 months (i.e. azathioprine 2–2.5 mg/kg/day or mercaptopurine 1–1.5 mg/kg/day in the absence of leukopenia), and/or
 - Active disease despite corticosteroids treatment (prednisolone up to 0.75 mg/kg/day) over a period of 4 Weeks, and/or
 - Active disease or relapse in spite of adequate treatment (as defined in the SmPC) with tumor necrosis factor [TNF] inhibitors or vedolizumab, and/or
 - Active disease or relapse in spite of adequate treatment with JAK inhibitors over a period of at least 6 Weeks.
- Patients receiving oral corticosteroids must have been on a stable dose of prednisone or prednisone equivalent (≤ 20 mg/day) or on beclomethasone dipropionate (≤ 5 mg/day) or on budesonide MMX (≤ 9 mg/day) for at least 2 Weeks prior to the screening visit;
- Topical corticosteroids and topical 5-aminosalicylic acid preparations must have been withdrawn at least 2 Weeks prior to the screening visit;
- Patients who are on oral 5-aminosalicylic acid must have been on a stable dose for at least 4 Weeks prior to the screening visit;

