 - The change from screening in Modified Mayo scores and Partial Mayo scores during the study.

In this mixed model, treatments and stratum will be fixed effects, subject will be random effect and baseline values of the respective measurements will be covariates. Other explanatory variables will also be allowed to be included in the model. To normalize eventual skewed distributions transformation of the data will also be considered. Study treatment groups will be compared within this model framework. All p-values will be interpreted in a descriptive manner.

The following subgroups will be analyzed:

- Gender
- Age
- Country
- US vs non-US
- Baseline MMS
- With/without previous biological or JAK inhibitors treatment
- Week 16 ABX464-NGlu AUC0-12 level above/below 7 000 h*ng/mL (vs. placebo)
- Concomitant UC medications.

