15.1.3. PRIMARY ANALYSIS OF PRIMARY EFFICACY VARIABLE

The primary efficacy analysis will be performed for FAS and PPAS.

The primary objective of this study is to determine an optimal ABX464 dose to be used in moderate to severe active ulcerative colitis patients who have failed or are intolerant to immunomodulators, Anti-TNF α , vedolizumab, JAK inhibitors and/or corticosteroids by comparing the mean change from baseline in the MMS at Week 8 for the three ABX464 dose levels to the placebo. An analysis of covariance (ANCOVA) model will be used to assess these changes.

The ANCOVA model for Change from Baseline MMS at Week 8 will include the fixed treatment effect, the previous use of biological or JAK inhibitors effect and the covariate, baseline MMS and a random error term.

The assumptions that the random errors in the ANCOVA model are normally distributed with homogeneity of variances will be checked. If either the hypothesis regarding normality of errors or the hypothesis of equal variances is rejected at the 5% significance level a nonparametric ANCOVA using the ranked data will be performed to test for differences in the mean change from baseline. The least square means and confidence intervals from the parametric ANCOVA will also be presented.

The dose testing will commence with comparing the ABX464 50mg dose with placebo. If this is significant at a 5% two-sided level (i.e. $p < 0.05$) a comparison against placebo will be carried out at the ABX464 100mg dose. Again, if significance at a 5% level for this test is observed the procedure will be repeated at the ABX464 25mg dose. If in this sequence of comparisons of ABX464 dose levels to placebo one is not significant (i.e., $p \geq 0.05$) the additional comparisons to placebo will not be

Document: \\iedc-vnasc01\BIOSdata\Abivax\ABX464\FZA92720\Biostatistics\Documentation\SAP\ABX464-103_SAP_V2.0_10MAY2021

Author: [REDACTED]

Version Number:
Version Date:

2.0
10May2021

Template No.: CS_TP_BS016 Revision 5

Reference: CS_WI_BS005

Effective Date: 01Apr2018

performed. Should any of these comparisons with the placebo treatment group be significant, further exploratory testing of the dose groups against each other will be conducted at the same significance level. A global comparison of all active treatment groups vs placebo group will also be conducted.

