15.2.1.6. Reduction Relative to Baseline in Stool Frequency and Rectal Bleeding

Number and percentage of patients in each Mayo stool frequency category will be summarized at every study visit and the number of patients with reduction in stool frequency sub-score relative to baseline will be recorded. The stool frequency sub-score corresponds to the **average** of the 3 most recent daily stool frequencies prior to the visit, rounded to the nearest whole number. The normal stool frequency is subtracted from this average to obtain the Mayo stool frequency sub-score for a particular visit. Frequency of stools will be obtained from e-Diaries completed daily by the patient.

Descriptive statistics for stool frequency sub-score and its change from baseline will be presented by visit.

Document: \\iedc-vnasc01\BIOSdata\Abivax\ABX464\FZA92720\Biostatistics\Documentation\SAP\ABX464-103_SAP_V2.0_10MAY2021

Author: [REDACTED] Version Number: 2.0
Version Date: 10May2021

Template No.: CS_TP_BS016 Revision 5

Reference: CS_WI_BS005

Effective Date: 01Apr2018

The frequency sub-score will be calculated as described above. Reduction relative to baseline is defined in Section 6.6.

Number and percentage of patients in each rectal bleeding category will be summarized. The number of patients indicating an improvement in rectal bleeding sub-score from the baseline rectal bleeding sub-score will be recorded. The rectal bleeding sub-score corresponds to the **worst category** of the 3 most recent values prior to the visit.

Only days when both the number of stool and the rectal bleeding are available will be considered for the calculation. If some data are missing from the most recent consecutive 3 days preceding the visit, then data from the next closest days within 7 days before the visit will be used for calculation.

15.2.1.7. Reduction Relative to Baseline in pMMS at every Visit and MMS at Week 16

Partial MMS will be assessed at every visit, and MMS at Screening, Week 8 and Week 16. Partial MMS is the sum of the stool frequency and rectal bleeding sub-scores of the MMS.

The screening MMS will be used as baseline MMS. Day 1 pMMS will be used as baseline pMMS. Absolute scores and change from baseline will be summarized by treatment arm, and the number of patients with a reduction relative to baseline in the scores will be recorded. Reduction relative to baseline is defined in Section 6.6

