15.2.3.3. Analysis of Secondary Variables Measured Repeatedly Over Time

In addition to descriptive statistics as described in Section 15.2, mixed model repeated measures ANCOVA will be used to assess the following secondary variables:

- Change from screening in MMS to Week 8 and Week 16 and change from baseline to all post-baseline visits in pMMS during the study, by treatment group vs placebo group.
- The change from baseline in fecal calprotectin levels at Week 8 and Week 16.
- The change from screening in the histopathology/infiltrate (rectal biopsies) assessed by the Robarts Histopathology Index, the Geboes and Nancy Histology Scoring Scales at Week 8 and Week 16 (if available).

Mixed Model for Repeated Measures (MMRM) will be used to analyze change from baseline in MMS, pMMS, fecal calprotectin, RHI, Geboes and Nancy scores. Change from baseline at the specified Week

Document: \\ieedc-vnasc01\BIOSdata\Abivax\ABX464\FZA92720\Biostatistics\Documentation\SAP\ABX464-103_SAP_V2.0_10MAY2021

Author: [REDACTED]

Version Number: 2.0
Version Date: 10May2021

Template No.: CS_TP_BS016 Revision 5

Reference: CS_WI_BS005

Effective Date: 01Apr2018

will be analyzed by using a MMRM model with baseline value as a covariate, fixed effects for treatment group, exposure to previous biologics or JAK inhibitors, visit, visit by treatment group interaction and a random error term. For the MMRM model, the Kenward-Roger method for approximating the denominator degrees of freedom and correcting for bias in the estimated variance-covariance of the fixed effects will be used. This will be achieved by specifying the DDFM = KR option in the MODEL statement within PROC MIXED. An unstructured covariance will be selected initially, and if convergence is not achieved with this structure, the following covariance structures will be used in the order listed until convergence is achieved: Toeplitz (TOEP), Autoregressive (AR) and Compound Symmetry (CS).

The strata US vs non-US sites will not be included as a factor in the model as the stratification occurs only because US patients will not receive 100 mg dose of ABX464.

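### The MMRM in SAP 15.2.3.3 fits one baseline slope for all visits; a baseline-by-visit term would protect late-visit precision and the Week 16 contrasts at almost no cost

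*SAP*

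**What the plan says.** SAP 15.2.3.3 specifies a mixed model for repeated measures on change from baseline in MMS, pMMS, fecal calprotectin, RHI, Geboes and Nancy. Its terms are "baseline value as a covariate, fixed effects for treatment group, exposure to previous biologics or JAK inhibitors, visit, visit by treatment group interaction". Baseline is a main effect only. The rest of the model is flexible: "An unstructured covariance will be selected initially", with simpler structures only if the fit does not converge, and Kenward-Roger degrees of freedom.

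Protocol 9.2 describes the same mean structure ("baseline values of the respective measurements will be covariates") but leaves room for more: "Other explanatory variables will also be allowed to be included in the model". It also says of these models: "All p-values will be interpreted in a descriptive manner".

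On timing, SAP 15.2.1.7 states: "Partial MMS will be assessed at every visit, and MMS at Screening, Week 8 and Week 16". In this model pMMS therefore has five scheduled on-treatment visits after baseline (Days 8, 29, 57, 85 and 113), and the other five outcomes have two (Weeks 8 and 16). Under Protocol 3.1.1 and SAP 3.1, the Week 16 endoscopy and biopsies are done only if the Day 57 endoscopy sub-score is 2 or 3.

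The primary analysis is separate: "The ANCOVA model for Change from Baseline MMS at Week 8 will include the fixed treatment effect" (SAP 15.1.3).

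**The concern.** When the outcome is change from baseline, the baseline slope at a visit depends on the correlation between baseline and that visit and on the spread of the score at that visit. Both can change between Day 8 and Day 113. A single slope is then a compromise, and a visit whose true slope lies far from it is adjusted poorly.

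Two things are at stake. The first is precision: a poorly adjusted visit has a larger residual variance. The second is accuracy at Week 16. Patients who improve endoscopically by Week 8 have no Week 16 endoscopy by design and, if the drug works, more of them will be on active treatment. The model then infers their Week 16 value from baseline and Week 8, and a wrong baseline slope distorts that inference differently in the two arms.

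**Working it through.** **The plan's own figure.** No figure is given for the MMRM. The sample size in Protocol 9.4 reproduces without it. With 58 × 0.95 = 55 evaluable per arm, difference 2.5 − 1.0 = 1.5 and SD 2.1, the standard error is 2.1 × √(2/55) = 0.400. Then 1.5/0.400 = 3.75, and power per comparison is about 96%. The MMRM does not enter this calculation.

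**Inputs for the precision check.** All SDs and correlations are assumptions. Entry requires "Modified Mayo Score (MMS) of 5 to 9 inclusive (on a scale of 0-9"), which limits the baseline spread; baseline SDs of 1.1 (MMS) and 1.0 (pMMS) were assumed. Visit SDs were 2.1 and 2.2 for MMS at Weeks 8 and 16, and 1.2, 1.4, 1.5, 1.6 and 1.6 for pMMS. There were 58 patients per arm, complete normal data, residual correlation between visits of 0.5 or 0.7 (MMS) and 0.6 or 0.8 (pMMS), unstructured covariance and 300 simulated trials per setting.

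**Formulas.**
- Slope at visit t = ρ_t × SD_t / SD_b − 1.
- Excess variance from a common slope = (slope_t − common)² × SD_b² / [SD_t² × (1 − ρ_t²)].
- Standard error ratio = √(1 + excess).

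**Worked case.** Take pMMS with correlation falling from 0.70 to 0.20 and residual correlation 0.8. The slope is 0.70 × 1.2 − 1 = −0.16 at Day 8 and 0.20 × 1.6 − 1 = −0.68 at Day 113. The fitted common slope was −0.19, close to the Day 8 value, because generalised least squares favours the less variable early visits. Excess variance at Day 113 is (−0.68 + 0.19)² / (2.56 × 0.96) = 0.240/2.458 = 0.098, so the ratio is √1.098 = 1.048. The simulation gave 1.047.

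**Model-based SE, common slope divided by visit-specific slopes** (range over the two residual correlations):

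| Outcome | Assumed baseline correlation | First visit | Last visit |
|---|---|---|---|
| MMS | 0.5 to 0.4 | 1.000-1.001 | 1.001 |
| MMS | 0.5 to 0.3 | 1.002-1.003 | 1.007-1.009 |
| MMS | 0.6 to 0.2 | 1.002-1.008 | 1.037-1.055 |
| pMMS | 0.50 to 0.30 | 1.000 | 1.002 |
| pMMS | 0.70 to 0.35 | 1.001-1.003 | 1.009-1.015 |
| pMMS | 0.70 to 0.20 | 1.001-1.009 | 1.035-1.047 |
| pMMS | 0.80 to 0.15 | 1.002-1.010 | 1.074-1.110 |

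In the two steep pMMS settings Day 85 also loses something: 1.4-2.3% and 4.4-7.2%. For a contrast with 80% power, power becomes Φ(2.80/ratio − 1.96): about 79% at 1.01, 76% at 1.05 and 71% at 1.11. With complete data neither model showed systematic bias.

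**Week 16 with conditional endoscopy.** Assumptions: two arms; baseline SD 1.1; Week 8 and Week 16 SDs 2.0 and 2.2; correlation 0.6 between the two visits; true Week 16 difference 1.5 (borrowed from Protocol 9.4). Week 16 was missing when the Week 8 score was good, about 23% of placebo and 50% of active patients. Large-sample maximum-likelihood estimates:

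| Baseline correlation, Week 8 to Week 16 | Common slope | Visit-specific slopes |
|---|---|---|
| 0.5 to 0.4 | 1.54 | 1.50 |
| 0.5 to 0.3 | 1.61 | 1.50 |
| 0.6 to 0.2 | 1.77 | 1.50 |

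The overstatement is 0.04/1.5 = 3%, 0.11/1.5 = 7% and 0.27/1.5 = 18%. Repeat simulations put the last two rows at 1.60-1.63 and 1.75-1.81 for the common slope, with no clear bias when slopes were nearly equal.

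**The case against.** A common baseline slope is a legitimate model, not an error or a contradiction. The documents give no correlation, pMMS standard deviation or slope at any visit, so nothing in them shows that the link with baseline weakens. If the spread grows while the correlation falls, the two offset and the slope hardly moves. No decision rests on these models: the primary analysis is a one-visit ANCOVA and the p-values here are descriptive. All of this stands and limits the weight of the point.

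Ordinary dropout is also a weak argument. With about 10% baseline-dependent dropout, equal in both arms, a simulated common slope moved the Day 113 pMMS contrast by less than 0.01. A shift of 0.03-0.06, against a standard error near 0.34, appeared only when dropout depended on baseline in one arm and the baseline link weakened steeply. The bias argument therefore rests on the conditional Week 16 endoscopy, which the objection does not answer.

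A reader might infer three stronger things. The first is that precision is lost at the earliest visit too; under the unstructured covariance that the SAP specifies, the model-based loss there is 1% or less in every setting. The second is that weakening is established; it is only an assumption. The third is a patient equivalent on the base of all 244; each contrast compares one dose with placebo, about 61 + 61 = 122 patients.

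**Conclusion.** The point holds as a minor, nearly free improvement. One slope for all visits costs nothing if the slopes are equal, about 0-2% of the standard error under mild to moderate weakening of the baseline link, and 4-11% under steep weakening, mostly at the latest visit.

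For Week 16 MMS and histology the restriction can also bias the contrast when slopes differ. A true 1.5 came out between about 1.5 and 1.8, while visit-specific slopes stayed near 1.5. This rests on assumed correlations, normal data and a Week 8 score cutoff in place of the endoscopy sub-score rule. The real rule acts on one component of the score, so missing at random is only approximate. The simulation was scaled to MMS and carries over to RHI, Geboes and Nancy by analogy only. It does not concern pMMS or fecal calprotectin, whose Week 16 values do not depend on the endoscopy.

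A reader might infer that the primary result or the sample size is in doubt. Neither uses this model.

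**What to change.** In SAP 15.2.3.3, add a baseline-by-visit interaction to the fixed effects for pMMS, MMS, fecal calprotectin, RHI, Geboes and Nancy, before unblinding. It costs 1 extra parameter for each two-visit outcome (2 − 1) and 4 for pMMS (5 − 1), with about 244 patients randomized. Protocol 9.2 already allows further explanatory variables in this model. The covariance sequence and degrees-of-freedom method can stay as written.

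The term removes the slope restriction only. Week 16 MMS and histology results will still depend on the missing-at-random assumption created by the conditional endoscopy, and the report should say so beside those contrasts.

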5.2.3. Day 8, Day 29, Day 85 Visits

- Physical examination and vital signs;
- Body weight;
- Hematology and Biochemistry including coagulation parameters and troponin;

- Blood pregnancy test for all women of childbearing potential (D29 and D85 only);
- Blood sample for miR-124 (PAXgene® tube) and cytokines determination at Day 8 and Day 29 only;
- Check treatment compliance and review the patient e-Diary;
- Partial Modified Mayo Score;
- Population Pharmacokinetics blood samples pre-dose;
- Adverse Events reporting;
- Dispense study treatment (Day 29 and Day 85 only);
- Schedule next patient visits.

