5.2.4. Day 57 and Day 113 Visits

- IBD Questionnaire (as the first visit procedure);
- Physical examination and vital signs;
- Body weight;
- At Day 113, population Pharmacokinetics blood samples at either pre-dose, 1, 2, 4h and if possible 48 h (Day 115 only) or pre-dose, 0.5, 1.5, 3h and if possible 48 (Day 115 only);
- Hematology and Biochemistry including blood pregnancy test for all women of childbearing potential, coagulation parameters and troponin;
- Blood sample for miR-124 dosage (PAXgene® tube) and cytokines determination;
- 12-leads ECG;
- Fecal calprotectin;
- Sigmoidoscopy with rectal/sigmoidal biopsies (Day 113 endoscopy is conditional on the response at Day 57);
- Modified Mayo Score at Day 57 (and Day 113 if available; OR pMMS at Day 113 if Day113 endoscopy not performed);
- Check treatment compliance;
- Adverse Events reporting;
- Study treatment dispensation at Day 57 visit;
- Review the patient e-Diary;
- At Day 113, enrolment of patients willing to take part to the maintenance phase;
- Schedule next patient visits.

5.2.5. End of Study Visit (Within a week after last dose \pm 2 days)

This EoS visit applies to all premature discontinued patients and to patients not taking part to the maintenance study. Patients will perform an End of Study Visit (EoS) within a Week after last dosing (i.e D120 \pm 2 days if the patient completed the study and is not taking part in maintenance study). Patients will be treated according to the standard of care from the last day of study treatment.

Following examinations/procedures should be performed:

- Physical examination and vital signs;
- Body weight;
- Hematology and Biochemistry and a follow-up 3 Weeks later;
- Partial Modified Mayo Score;
- 12 leads ECG;
- Fecal calprotectin;
- Adverse Events reporting.

NB#1: In case of premature discontinuation occurring during the treatment phase (D1-D113), the above examinations should be performed as an End of Study Visit 7 days \pm 2 days after last dose.

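### SAP 15.2.3.3: every fallback covariance in the MMRM assumes equal variance at all visits, so if the unstructured fit fails and variances differ, visit-specific standard errors are biased, in a direction that depends on how variance changes over time (minor)

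*SAP*

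**What the plan says.** SAP section 15.2.3.3 covers six outcomes: "Mixed Model for Repeated Measures (MMRM) will be used to analyze change from baseline in MMS, pMMS, fecal calprotectin, RHI, Geboes and Nancy scores". The covariance rule starts with "An unstructured covariance will be selected initially, and if convergence is not achieved with this structure", and then lists, to be tried in order until one converges, "Toeplitz (TOEP), Autoregressive (AR) and Compound Symmetry (CS".

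Inference is model-based. The SAP uses "the Kenward-Roger method for approximating the denominator degrees of freedom and correcting for bias in the estimated variance-covariance of the fixed effects", implemented by "specifying the DDFM = KR option in the MODEL statement within PROC MIXED". It names no heterogeneous-variance structure and no empirical (sandwich) standard error at any step.

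Protocol section 9.2 describes the same analysis with a random subject effect and says that its p-values are to be read descriptively.

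**The concern.** In PROC MIXED, TOEP, AR and CS as named each estimate a single residual variance shared by all visits. The change in pMMS after one week need not have the same spread as the change after sixteen. If it does not, a common variance gives every visit a standard error based on the average spread. That is too large where the true spread is small and too small where it is large.

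Kenward-Roger adjusts for small-sample bias and degrees of freedom given the assumed structure. It does not detect or repair a wrong structure. The protocol's random subject effect does not help either, because it adds the same variance at every visit. Going down the list therefore never relaxes the equal-variance assumption.

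At stake are the visit-by-visit pMMS contrasts with placebo, which serve a stated secondary objective and bear on onset and on the Week 16 effect by dose. Even with descriptive p-values, readers will use the confidence intervals, which come from the same standard errors.

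**Working it through.** **Plan's own figure.** There is none to reproduce. The only SD in the documents is 2.1, the pooled SD of the change in MMS at Week 8 (Protocol 9.4). No SD is given for pMMS or for any other visit.

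**Inputs from the documents.** The post-baseline pMMS visits are Days 8, 29 and 85 (Protocol 5.2.3, "Day 8, Day 29, Day 85 Visits") and Days 57 and 113 (Protocol 5.2.4, "Day 57 and Day 113 Visits"), with an end-of-study visit for some patients. MMS, calprotectin and histology enter the model at Weeks 8 and 16 only. The plan has 61 patients per arm.

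**Size of the unstructured model.** T visits need T(T+1)/2 covariance parameters:
- two-visit outcomes: 2×3/2 = 3
- pMMS: 5×6/2 = 15, or 6×7/2 = 21 if the end-of-study visit is included

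With about 244 patients, failure looks unlikely. The SAP does not say whether the end-of-study visit, which is sparse, is a level in the model.

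**Formula.** With complete data, a common-variance fit estimates roughly the mean of the visit variances (exactly so for CS). For visit j:
- r_j = model SE / true SE = √(mean of SD²) / SD_j
- actual rejection rate of a nominal 5% test = 2[1 − Φ(1.96 r_j)]

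The number per arm cancels from r_j.

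**Worked example, assumed residual SDs 1.2, 1.45, 1.65, 1.75, 1.8.** The squares are 1.44, 2.1025, 2.7225, 3.0625 and 3.24. They sum to 12.5675, the mean is 2.5135 and the common SD is 1.585.
- Day 8: r = 1.585/1.2 = 1.32, rejection 2[1 − Φ(2.59)] ≈ 1%
- Day 113: r = 1.585/1.8 = 0.88, rejection 2[1 − Φ(1.726)] ≈ 8.4%

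**Other assumed patterns, same formula:**

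| Residual SD, Days 8 to 113 | Common SD | r, Day 8 | r, Day 113 | Rejection, Day 8 | Rejection, Day 113 |
|---|---|---|---|---|---|
| Rising, 1.2 to 1.8 (above) | 1.585 | 1.32 | 0.88 | 1% | 8.4% |
| Mild rise, 1.4 to 1.7 | about 1.58 | 1.13 | 0.93 | 2.7% | 6.8% |
| Flat, 1.6 | 1.60 | 1.00 | 1.00 | 5% | 5% |
| Peak then fall: 1.2, 1.7, 1.7, 1.5, 1.4 | 1.512 | 1.26 | 1.08 | 1.4% | 3.4% |
| Falling: 1.8, 1.7, 1.6, 1.5, 1.4 | 1.606 | 0.89 | 1.15 | 8.0% | 2.5% |

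**Checks on the formula.**
- Numerical fits of TOEP, AR(1) and CS to the falling pattern agree closely: TOEP gives 0.89 at Day 8 and 1.15 at Day 113. For the peaked pattern TOEP gives 1.22 and 1.05. With 20% dropout the directions do not change.
- In 400 simulated four-arm trials under the 1.2 to 1.8 pattern with about 10% dropout, TOEP gave ratios of 1.33 at Day 8 and 0.87 at Day 113, with 10.0% rejection at Day 113. The Monte Carlo standard error there is √(0.1×0.9/400) = 1.5 points, so this agrees with 8.4%.

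**Two-visit outcomes.** TOEP, AR and CS are then one and the same model.
- SD from 2.1 to 2.4: common SD √((4.41+5.76)/2) = 2.255, so r = 1.07 at Week 8 and 0.94 at Week 16
- SD from 2.1 to 1.8: common SD √((4.41+3.24)/2) = 1.956, so r = 0.93 and 1.09

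**Heterogeneous structures.** Across five assumed pMMS patterns (rising, mildly rising, flat, peaked, falling), with and without 20% dropout, r at every visit was 1.00 for TOEPH, 1.00 for ARH(1) (at most 1.004) and 0.97 to 1.03 for CSH.

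**The case against.** The strongest objection is about direction. A reader might infer that once the unstructured fit fails, early intervals are always too wide and Week 16 intervals too narrow. The documents do not support that, because they give no variance by visit. They also contain reasons why late spread might shrink. pMMS is bounded at 0 to 6, and patients who worsen leave the study from Week 8. For MMS, only patients without endoscopic improvement at Day 57 have a Week 16 endoscopy; in an illustrative simulation with equal SDs of 2.1, that selection reduced the observed Week 16 SD to between 1.94 and 2.04. On the other side, the model adjusts for baseline, and correlation with baseline should weaken over time. Even with a flat raw SD, an assumed correlation falling from 0.6 to 0.3 gives an early/late residual SD ratio of √(1−0.36)/√(1−0.09) = 0.84. Rising variance is plausible for pMMS, but it is an assumption.

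A reader might also blame the unequal visit gaps (21, 28, 28 and 28 days). That does not carry weight: CS makes no spacing assumption and gave nearly the same ratios as TOEP and AR, and TOEPH and ARH(1) share the spacing assumption.

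Three limits on importance stand in full. The fallback applies only if the unstructured fit fails, which looks unlikely. The primary Week 8 MMS test is an ANCOVA (SAP 15.1.3), and the gatekeeping in SAP 7.4 does not rest on the MMRM. SAP 15.2 also reports SDs by visit and arm, so unequal variances would be visible. None of this answers the core point that the plan, having provided for failure, lists only structures with the same restriction.

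**Conclusion.** The point holds as a minor defect in a contingency rule. If the unstructured fit fails and visit variances differ, the standard errors and intervals for the visit-wise pMMS contrasts are biased. The direction follows the variance pattern, and equal variances give no bias.

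Under the two assumed rises, the Week 16 standard error is about 7% or 12% too small. These sizes rest on assumed SDs and on the fallback being reached. If the unstructured fit converges, nothing changes, and no confirmatory conclusion depends on it.

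**What to change.** In SAP 15.2.3.3, replace the fallback order with TOEPH, then ARH(1), then CSH, keeping Kenward-Roger. If none converges, use CS with empirical (sandwich) standard errors, without Kenward-Roger. Make the change before unblinding, so that it is not a post-hoc choice.

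The cost is a few words and one TYPE= option per step. For pMMS with five visits there are four more variance parameters (five variances instead of one), and a slightly higher chance that a given step does not converge. For two-visit outcomes, two variances and one correlation are the same three parameters as the unstructured matrix, so the sandwich step is the only real fallback there.
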